5.7 Treatment compliance

The administration of all medication (including IP) should be recorded in the appropriate sections of the eCRF.

Treatment compliance, both regarding background metformin treatment and IP, will be assessed by tablet count. To be eligible for randomization, patients must have taken at least 75 % of their metformin tablets during the run-in period. In the statistical analysis, acceptable compliance is defined as having taken at least 75 % of the metformin doses and at least 75% of the IP doses during the randomized treatment period. Treatment compliance will be calculated as follows:

$$\text{Compliance} = \frac{\text{number of tablets dispensed} - \text{number of tablets returned}}{(\text{date of last dose} - \text{date of first dose} + 1) \times \text{number of tablets}}$$

The number of tablets in the calculation is the number of tablets that patients should have received each day, as per protocol.

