Glipizide will be encapsulated into orange hard gelatine capsules and contain glipizide tablets corresponding to a dose of 5mg glipizide or no glipizide tablets if a placebo capsule. The total daily dose of glipizide/ placebo will be composed of 4 capsules, of which up to 4 capsules will contain active compound and rest placebo, depending on the daily dose.

Two tablets AZD1656 and two capsules glipizide will be administered orally in the morning with breakfast and 2 tablets AZD1656 and 2 capsules glipizide will be administered orally in the evening with dinner. Patients randomized to the blinded treatment will take both AZD1656/placebo and glipizide/placebo. Patients assigned to the open dose of AZD1656 will only take 2 tablets of AZD1656 at each dosing event.

Two strengths of metformin tablets, 500mg and 850mg respectively, will be provided by the sponsor. The metformin will be packed in to blister cards, open-label, 100 tablets per package for the 500mg metformin and 56 tablets per package for the 850mg metformin. The dose will be individual but will stay between 1.5 and 3 g per day, administered orally as tablets once, twice or three times daily together with meal.

Duration of study and randomized treatment period

An enrolment visit (screening) will take place approximately 4 weeks before the start of randomized study treatment. Eligible patients will receive randomized treatment for 4 month and those patients consenting also to the 2-month extension will receive randomized treatment for 6 months in total. During the randomized treatment period, visits to the clinic are scheduled on a weekly basis during the initial titration period, followed by visits each month during the maintenance phase up to 4 months, with an optional 2 months extension. A follow-up visit will be scheduled 2 weeks \pm 5 days after the end of treatment visit (or last visit if premature discontinuation).

Outcome variable(s):

Primary outcome variable

- The primary efficacy variable is defined as the change in HbA1c from baseline to the final visit at 4 months. Baseline will be defined as the last non-missing value on or before the first treatment dose received (the HbA1c sample at Visit 3 will be collected prior to the first dose intake). If the value is missing at the randomization visit, the enrolment (screening) result will be used.

Secondary outcome variables

- The time-course of drug concentrations for AZD1656 and its active metabolite AZD12555623 in plasma.

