1.2 Research hypothesis

This study will investigate if AZD1656 on top of metformin is superior to placebo on top of metformin, in terms of the change in HbA1c from baseline to the final visit at 4 months in T2DM patients not adequately controlled on metformin alone.

Furthermore, the study will evaluate the safety profile of AZD1656 in the investigated dose ranges and whether AZD1656 has a predictive pharmacokinetic (PK) profile in a patient population similar to future target populations.

In addition, this study will investigate that AZD1656 on top of metformin has favourable effects on other parameters of glucose control (eg, fasting and post-prandial glucose levels) compared to placebo, and if AZD1656 has no negative effects on cardiovascular risk factors such as lipid metabolism.

The safety and efficacy (only explorative analysis) of AZD1656 on top of metformin will also be compared to treatment with glipizide on top of metformin. In addition, the safety and tolerability of AZD1656 in patients with severely impaired glucose control will be explored during a 4 months, with an optional 2-month extension, treatment period. The results of the active comparator arms will also indicate the validity of the study outcome.

Genetic samples will also be collected in the study to enable future exploratory research in to genes/genetic variation that may influence response (ie, distribution, safety, tolerability and efficacy) to AZD1656, metformin, and glipizide.

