5.5 Treatments

5.5.1 Identity of investigational products and metformin

AZD1656 and placebo will be administered as white, round tablets. The tablets will contain AZD1656 corresponding to the strength 5mg, 20mg, 50mg of the active compound respectively or placebo. The tablets will be packed into blister cards to achieve the intended dose. Each dose of AZD1656 will be composed of 2 tablets. The patient will take half of the daily dose in the morning and half of the daily dose in the evening.

Glipizide will be encapsulated into orange hard gelatine capsules and contain glipizide tablets corresponding to a dose of 5mg glipizide. The capsules will be packed into blisters of 5, 10, 15 or 20mg of glipizide or placebo. Each daily dose of glipizide will be composed of 4 capsules. When 5mg or 15mg is given as the total daily dose, the largest dose should be taken in the morning.

Patients randomized to either of the blinded arms of AZD1656 or glipizide will take two tablets AZD1656 and two capsules glipizide orally in the morning with breakfast and 2 tablets AZD1656 and 2 capsules glipizide will be administered orally in the evening with dinner. Patients fulfilling the criteria for open-label AZD1656 arm will only take two tablets of AZD1656 at each dosing event.

A wallet, consisting of a blister card of AZD1656 dose 10, 20, 40, 50, 100, 140, 200mg or placebo and a wallet consisting of a blister card of glipizide 5, 10, 15, 20mg or placebo, will be created. In total, 13 different wallet combinations will be created. AZD1656 and glipizide will be administered twice daily together with breakfast and dinner. The patient will take 2 tablets of AZD1656 and 2 capsules glipizide at each administration. Patients randomized into either of active arms of AZD1656 will take glipizide placebo and vice versa.

The number of kits to be distributed for patients receiving AZD1656 and glipizide is presented in [Table 3](#).

Table 3 Number of kits per visit for patients on AZD1656 and glipizide

Visit	AZD1656	Glipizide
2	-	-
3	1	1
4	1	1
5	1	1
6	1	1
7	4	4
8	4	4
9	4	4
10	4	4
Extension: visit 12	4	4

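### The compliance formula in section 5.7 counts tablets only, so in the glipizide arm it measures placebo tablets and not the capsules that carry the drug

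*Protocol*

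**What the plan says.** Section 5.7 of the protocol sets the method: "Treatment compliance, both regarding background metformin treatment and IP, will be assessed by tablet count". The formula divides tablets dispensed minus tablets returned by days on treatment times tablets due per day. On the last term the section says: "The number of tablets in the calculation is the number of tablets that patients should have received each day, as per protocol". For the statistical analysis, acceptable compliance means having taken "at least 75 % of the metformin doses and at least 75% of the IP doses during the randomized treatment period".

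Section 5.5.1 describes two dosage forms. AZD1656 and its placebo are tablets. For the comparator: "Glipizide will be encapsulated into orange hard gelatine capsules and contain glipizide tablets corresponding to a dose of 5mg glipizide". On the twice-daily dosing: "The patient will take 2 tablets of AZD1656 and 2 capsules glipizide at each administration". On the double dummy: "Patients randomized into either of active arms of AZD1656 will take glipizide placebo and vice versa". The synopsis adds that the daily total is four capsules, "of which up to 4 capsules will contain active compound and rest placebo, depending on the daily dose". Cohort 2 patients take open-label tablets only.

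Compliance is used in two places. Section 12.1.1 lists non-compliance among the major deviations that remove a patient from the per-protocol set. Section 12.2.5 has compliance derived for each patient over the whole exposure.

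**The concern.** The formula counts one dosage form in a trial where each blinded patient takes two, and the counted form carries no active drug in one of the arms. For glipizide patients the compliance figure then describes how well they took dummy tablets. The error runs both ways: a patient who takes no glipizide can be classed as compliant, and one who takes every capsule but neglects the tablets can be classed as non-compliant.

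The glipizide arm has an interpretive role. Section 1.2 says: "The results of the active comparator arms will also indicate the validity of the study outcome". If glipizide showed less effect than expected, a natural first question would be whether it was taken. Section 6.6.1 plans plasma assays for AZD1656 and its metabolite only, so for glipizide the returned-capsule count is the main objective evidence of intake, and the compliance formula does not use it.

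**Working it through.** **Inputs**
- Cohort 1 size: four arms of about 90 and two fixed-dose arms of about 45 (synopsis), so 4 × 90 + 2 × 45 = 450. This agrees with the 450 in section 3.1. Glipizide share: 90/450 = 20%.
- Units due per day in cohort 1: 2 tablets + 2 capsules, twice daily = 4 tablets + 4 capsules = 8 units (section 5.5.1).
- Threshold: 75% (section 5.7). This is a rule, not a derived figure, so there is nothing to reproduce.
- Active capsules per day in the glipizide arm: 1, 2, 3 or 4 of 4 at 5, 10, 15 or 20 mg (synopsis and Table 1).
- Illustrative exposure of 120 days (Visit 10 in Table 2). The percentages do not depend on this choice.

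**Reading A: the formula as written, tablets only.** A glipizide patient takes every tablet and no capsule.
- Compliance = (120 × 4) / (120 × 4) = 480/480 = 100%. Glipizide taken: none.
- Reverse case, every capsule and no tablet: 0/480 = 0%. Glipizide taken: all.

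In the AZD1656 arms the same formula counts the form that carries the active drug, so this fault does not arise there.

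**Reading B: tablets taken to mean any unit, both forms pooled.** All dummy units are taken, plus half of the active-form units.
- Compliance = (480 + 240) / (120 × 8) = 720/960 = 75%, which meets the threshold.
- This applies to any active arm: all capsules plus half the tablets on AZD1656, or all tablets plus half the capsules on glipizide.
- With two of four capsules missed daily, the least active glipizide a passing patient could take is max(0, a − 2)/a, where a is the number of active capsules: 0 at 5 mg (a = 1), 0 at 10 mg (a = 2), 1/3 at 15 mg (a = 3) and 1/2 at 20 mg (a = 4).

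**Reading C: each form counted separately, 75% of each required.**
- The Reading A patient has capsules 0/480 = 0% and fails.
- The Reading B glipizide patient has capsules 240/480 = 50% and fails.
- Remaining slack: one of four capsules may be missed daily. If it is always an active one, the active share taken is (a − 1)/a: 0 at 5 mg, 1/2 at 10 mg, 2/3 at 15 mg and 3/4 at 20 mg.

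The three readings give different pass or fail results for the same patient.

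**The case against.** The best defence is that tablet is loose wording for a dispensed unit. The acceptance rule speaks of IP doses, IP includes glipizide and its placebo, and the capsules are said to contain glipizide tablets. On that view a patient who takes no capsules has not met the rule. This has some force, but it shows that the rule and the formula disagree; it does not supply a capsule term. It also leaves open whether the forms are pooled or counted separately, and the result depends on that. Counting the tablets inside the capsules is not workable, because placebo capsules contain none.

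Other objections stand and set the size of the point:
- The primary analysis uses the full analysis set with LOCF, and its model has five levels without glipizide (synopsis). Section 12.2.6.2 places the glipizide comparisons among the exploratory ones done on that set only. Section 12.2 says that the study is not powered for glipizide against AZD1656.
- Pooling is a possible reading, not stated text.
- Capsule counts are not lost. Section 5.7.1 and the accountability rows of Table 2 cover all study drug.
- Taking every tablet and no capsule is a worst case, since both are taken at the same meals. The documents give no basis for estimating how many patients would be misclassified.

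A reader might infer from the validity statement in section 1.2 that the fault undermines the glipizide comparison or the trial's result. The documents do not support that, because compliance does not enter those planned analyses and the capsule data exist.

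A reader might also object that the formula treats 500 mg and 850 mg metformin tablets as equal. This matters only if a patient consistently drops the 850 mg tablet, and only in two of the eight regimens in Table 4: at 2700 mg, 3/4 = 75% of tablets but 1850/2700 = 68.5% of the milligrams; at 2850 mg, 4/5 = 80% but 2000/2850 = 70.2%. Nothing in the protocol suggests such selective dropping, so it is too minor to press.

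**Conclusion.** The point holds, with limited effect. As written, the formula leaves out the only dosage form that carries active drug for 20% of randomized patients and can score a glipizide non-taker at 100%, against the section's own 75% rule. The consequences are confined to the compliance summaries and to which patients, mainly in the glipizide arm, enter the supportive per-protocol set. Under the tablets-only reading, compliance in the AZD1656 arms is based on the right form; it would be diluted there only if the forms were pooled.

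This rests on taking tablet and capsule as the distinct products that section 5.5.1 makes them, and on the planned arm sizes. The correction is worth making because it is specific and almost free, not because an efficacy conclusion depends on it.

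**What to change.** In section 5.7, apply the existing formula twice for IP in cohort 1: once to tablets (4 due daily) and once to capsules (4 due daily). In cohort 2, apply it to tablets only. Report both figures and define acceptable IP compliance as at least 75% of each. Every cohort 1 patient is due the same number of each form at every dose step, so the rule can be applied blind.

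The cost is one formula and its programming; section 5.7.1 and Table 2 already provide the counts. There are two downsides. Some AZD1656 patients who miss only dummy capsules will leave the per-protocol set. At glipizide doses below 20 mg some capsules are placebo, so the capsule count remains an approximate measure of active drug taken; the protocol should say so.

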5.7.1 Accountability

The study drug provided for this study will be used only as directed in the study protocol.

The study personnel will account for all study drugs dispensed to and returned from the patient.

The study personnel will account for all received study drugs and return all unused study drugs. At the end of the study, all used and unused study drug will be returned for destruction by the study monitor. Documentation of drug accountability and drug destruction return will be maintained by the site.

All sites will receive training regarding appropriate procedures for drug ordering, accountability and return.

5.8 Discontinuation of investigational products

Patients may be discontinued from IP in the following situations:

1. Patient decision. The patient is at any time free to discontinue treatment, without prejudice to further treatment.
2. AE.

3. Severe non-compliance to study protocol as judged by the investigator and/or AZ/ICON Clinical Research.
4. Risk to patients as judged by the investigator and/or AZ
5. Patient lost to follow-up.
6. Incorrectly randomized patient, see Section 3.1.

Development of any study specific criteria will lead to discontinuation from IP:

- Patient uses amiodarone, warfarin, rimfampicin or potent CYP450 inhibitors, such as, but not limited to, ketokonazole and macrolide antibiotics during the study should be discontinued from the study.
- Patients who despite dose reduction of IP once, experiences more than one major hypoglycaemic event with need for external assistance due to impaired consciousness, or with other hypoglycaemic event(s) resulting in safety concerns with continued IP treatment, should be discontinued from the study. The hypoglycaemic event should be recorded in the appropriate CRF modules.
- Patients with remaining hyperglycemia despite maximum tolerable dose of basal night-time insulin, according to the investigator, should be discontinued from the study and receive appropriate glucose corrective treatment. For the definition of hyperglycemia at different time points during study, see section 5.6.1
- Patient who develops a condition contraindicating treatment with metformin or glipizide during the study should be discontinued. Conditions include, but are not limited to, renal impairment with GFR <60 ml/min, shock and diabetic ketoacidosis. However, temporary discontinuation of metformin and/or IP (up to 7 days) due to e.g. acute illness or radiological investigations with iodinated contrast media is allowed
- Increase in plasma CK levels to more than 10 x ULN on two consecutive measurements that cannot be ascribed to a benign condition or situation.
- Increase in AST and or ALT to more than 5 x ULN
- ALT or AST more than 3 x ULN and total bilirubin more than 1.5 x ULN.

5.8.1 Procedures for discontinuation of a patient from investigational product

All discontinuation due to hypoglycaemia should be according to the judgement of the investigator, ie, the investigator should be able to allow the patient to continue (even after a major hypoglycaemic event) if there are clear circumstances explaining the event, and the risk for a recurrence is low.

If the patient is discontinued from IP, the patient is also discontinued from the study. As far as possible they will be seen and assessed by the investigator at an end of study visit and then at a follow-up visit scheduled according to the study protocol and including the procedures described in Section 5.8.1. If the patient does not agree to this option, a modified follow up (eg, telephone contacts) should be arranged, if agreed to by the patient and in compliance with local data privacy laws/practices. The approach taken should be registered in the eCRF. Follow-up is not applicable if the patient is lost to follow-up.

For patients discontinuing due to liver enzyme criteria, special evaluation will be performed, see [Appendix E](#).

If a patient is to be withdrawn from the study, see Section 5.9.

5.9 Withdrawal from study

Patients are at any time free to withdraw from study (IP and assessments), without prejudice to further treatment (withdrawal of consent). Such patients will always be asked about the reason(s) and the presence of any adverse events. If possible, they will be seen and assessed by an investigator. Adverse events will be followed up (See Sections 6.4.3 and 6.4.4); the Patient Diary and study drug should be returned by the patient. The investigator and AstraZeneca/ICON may withdraw patients from the study (IP and assessments) due to safety reasons. Patients withdrawn from study will not be replaced.

6. COLLECTION OF STUDY VARIABLES

6.1 Recording of data

The Rave Web Based Data Capture (WBDC) system will be used for data collection and query handling. The investigator will ensure that data are recorded on the electronic Case Report Forms (eCRF) as specified in the study protocol and in accordance with the instructions provided.

The investigator ensures the accuracy, completeness and timeliness of the data recorded and of the provision of answers to data queries according to the Clinical Study Agreement. The investigator will sign the completed eCRF. A copy of the completed eCRF will be archived at the study site.

6.2 Data collection

For full details please see the study plan ([Table 2](#)) and the eCRF manuals.

6.3 Efficacy

6.3.1 Efficacy variables related to glucose control

6.3.1.1 HbA1c

Samples for HbA1c analysis will be collected at the enrolment visit (screening; Visit 1), the randomization visit (Visit 3), and monthly after the titration period (from Visit 7), see [Table 2](#).

6.3.1.2 FPG

Samples for fasting plasma glucose will be collected and analysed immediately at the clinic at every visit (except for Visit 2), see [Table 2](#). At each visit, a venous sample for analysis of FPG will also be sent to the central laboratory. The FPG samples, both the 1 analysed immediately at the clinic and the 1 for the central laboratory, should be taken when the patient is fasting, and before the IP is administered.

6.3.1.3 SMPG measurements

All patients will receive life-style advice and glucometers from 2 weeks prior to randomization onwards and will be asked to check their plasma glucose on a regular basis at home during the study, registering the results in a Patient Diary. The diary will be utilised from Visit 2 before randomization onwards. Between Visit 2 and 3, and during the titration weeks, at least 1 fasting morning plasma glucose and 1 bed-time plasma glucose assessment are needed on a daily basis and within 3 days prior to each of Visit 3, 4, 5, 6 and 7, a 7-point glucose assessment should be completed and results registered in the Patient Diary. During the maintenance period, after Visit 7 and onwards, plasma glucose checks are not required on a daily bases at home, but patients are requested to collect a 7-point glucose assessment within a 5-day window before each visit to the clinic (ie, before Visits 8-10). Patients entering the extension period are requested to collect a 7-point glucose assessment within a 5-day window before the extension visits.

Patients will be carefully instructed to register any episode with symptoms suspected being related to low plasma glucose levels. The Patient Diary will be reviewed by the investigator at each study visit and any low plasma glucose values and episodes considered as hypoglycaemic events will be transferred into the CRF. The 7-point assessment should include the following time points:

- Fasting before breakfast.
- 2 hrs after breakfast.
- Before lunch.
- 2 hrs after lunch.
- Before dinner.
- 2 hrs after dinner.

- At bed-time.

During the titration period, the decision to increase the dose will be based on SMPG data and the FPG measured at the clinical visit (see Section 3.1). The study staff will transfer the 7-point data and any hypoglycaemic event from the Patient Diary to the eCRF. The morning and bedtime glucose results and any additional glucose checks requested by the investigator will not be transferred to the eCRF, those measurements are used for the investigator's safety monitoring of the patient.

6.3.1.4 OGTT

An oral glucose tolerance test with collection of blood samples during 2 hours will be performed at baseline (Week 0, Visit 3) and 4 months (Visit 10) in a subgroup of the study population. At baseline (Week 0, Visit 3), after an overnight fast, patients will receive 75 g glucose orally, dissolved in water. Blood samples will be collected pre-dose and at 30 - 60 - 90 - 120 minutes post glucose intake for the analyses of plasma glucose, insulin, C-peptide and pro-insulin. IP will taken together with breakfast after the last OGTT sample at 120 minutes. At 4 months (Visit 10), after an overnight fast and 15 minutes after administration of the IP morning dose (no IP at baseline visit) at the clinic, patients will receive 75 g glucose orally, dissolved in water. Blood samples will be collected pre-dose and at 30, 60, 90 and 120 minutes post glucose intake for the analyses of plasma glucose, insulin, C-peptide and pro-insulin. Breakfast will be served immediately after the last OGTT sample at 120 minutes. The OGTT will be performed at selected sites. Countries that not will take part of the OGTT are Chile, Hungary, UK and Sweden.

